### **3. Study Design**

We plan to perform an unmasked, non-inferiority randomized controlled trial to determine if the quality of life is improved with the use of TENS compared to PTNS for urgency urinary incontinence and overactive bladder. The target population is patients with OAB and/or urgency urinary incontinence (UUI) who present to the urogynecology clinic either at the University of New Mexico Hospital (UNMH) or Sandoval Regional Medical Center (SRMC). Women will be informed of the arm of the study to which they are randomized, as the intervention is unable to be masked. Masking is not possible with this study design due to the nature of the interventions. All women will give written consent prior to enrollment.

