participation in the study or outcome measurement will not be extended further than 13 weeks after randomization. However, they will not be withdrawn from the study for missing sessions, and will be followed for outcomes and adverse events despite missing sessions of PTNS. Women that miss more than one session of PTNS or miss one session and do not make it up at the end will be considered “not fully compliant” with PTNS treatment, and will be analyzed in the “intention-to-treat” analysis in the PTNS arm but not in the “per protocol” analysis in the PTNS arm.

Prior to their week 6 session, women will be asked to complete a 3-day voiding diary in the three days before their scheduled PTNS treatment and bring it to clinic. At their week 6 session, women will complete the UDI and PSQ questionnaires via REDCAP on an iPad in clinic. The same will be conducted for their week 12 session. Patient compliance of attending PTNS sessions will be recorded.

**12.1.2. TENS:** Women randomized to the TENS groups will begin therapy after their baseline evaluation is complete. They will be asked to purchase a TENS 7000 device (estimated cost \$30) and will administer self-treatment at home, daily for 20 minutes, for 12 weeks total. Current practice in the Urogynecology clinic is to offer TENS therapy to women as an alternative to in-person maintenance therapy for after completing PTNS 12 sessions. TENS 7000 device is off label for its use in the treatment of OAB. If funding is secured, women in both PTNS and TENS group will be reimbursed with a merchandise card. Participants will be asked to bring their device to clinic to ensure the correct device is used, standardize settings and provide the following patient education:

- Proper TENS device set up and pre-set standardized settings, detailed below
- Proper electrode pad placement that will be demonstrated. Electrodes will be traced with a skin marker during this clinic visit and pictures will be provided to ensure correct placement at home. If the patient has a camera, they can photograph electrode placement while in clinic.
- Determine intensity level
- Patients will be notified that they can go about their regular daily activities with the TENS device in place, so that treatment does not interfere with normal work or household duties. However, they will be instructed to not use the device while exercising due to sweat causing reduced adhesive function of electrodes and possible displacement.

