### 13.Data Analysis

- 13.1. *Data Analysis:* Between and within group differences will be evaluated using Fisher's exact test for categorical variables and t-tests for continuous variables, as we expect the data will be normally distributed. Wilcoxon rank-sum test will be used for continuous variables that are not normally distributed. If there are any baseline differences between groups, a multivariate analysis will determine the contribution of these differences to observed differences (if any) between groups.
- 13.2. *Intention-to-treat analysis:* We plan to perform the primary analysis as "intention-to-treat" indicating that patients will be analyzed in the group to which they were randomized, regardless of compliance with study procedures, unless they asked to be withdrawn or were withdrawn by investigators due to safety or validity concerns. For example, PTNS patients that miss more than one session or do not make up a missed session of their office PTNS would still be analyzed in the "intention-to-treat" analysis as being in the PTNS group.
- 13.3. *Per protocol analysis:* We plan to perform a secondary analysis as "per protocol" indicating that patients will be analyzed in the group to which they were randomized only if they complete a full 12 weeks of treatment in compliance with study procedures, meaning that women assigned to the PTNS arm completed 12 weekly PTNS sessions in the office in 13 weeks or less, and women in the at-home TENS arm performed TENS stimulation at least 5 days per week for 12 weeks, as averaged over 12 weeks. For example, PTNS patients that miss more than one session or do not make up a missed session of their office PTNS will not be analyzed in the "per protocol" analysis as being in the PTNS group.
- 13.4. *Power Analysis:* Power analysis was performed based on previously reported means and standard deviation for the OAB-q. The primary outcome of this study is improvement in HRQL and symptom bother of OAB/UUI as measured by the OAB-q. We used the means and standard deviation for this questionnaire from a prior unpublished pilot RCT from Walter Reed comparing PTNS and TENS for the treatment of OAB. We have assumed a change score of greater than 10 points to be significant between groups based on the minimally important difference that has been previously established. To achieve significance for a non-inferiority study using these assumptions we would need 80 patients,

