#### **15. Withdrawal of Subjects**

Participants may withdraw from the study at any time without penalty and will continue to receive the clinical standard of care. A subject may be withdrawn from the study without her consent at the discretion of the physician and study staff if they believe she no longer meets study inclusion criteria or if she meets exclusion criteria, if they believe that it is not in her best interest to continue study participation i.e., desire to undergo alternative treatment, or if they stop the study early due to scientific reasons. Investigators may withdraw a subject if the subject is not following the study protocol. If a woman is withdrawn from the study either at her own discretion or that of the research staff, she may continue with conservative or surgical management of her OAB/UUI in the usual fashion. If a participant chooses to withdraw from the study, the study intervention and PTNS device will no longer be provided to the participant and may not be available for purchase. If a participant withdraws from the TENS group, the TENS device they purchased will be kept by the participant.

To minimize withdrawal from the study, patients will be randomized after they have had what they feel to have been adequate time to consider whether or not they would like to participate in the study and they provide consent. According to the 2010 CONSORT guidelines, we will analyze all participants assessed for eligibility within the study. We will document reasons for withdrawal from the study if the participant willingly provides this

PROTOCOL TITLE: INTENSE: INvestigation of TENS Efficacy versus Posterior Tibial Nerve Stimulation for overactive bladder

information. We will report eligibility criteria not met or reasons for declining participation in the study if the participant willingly provides this information. The withdrawal procedure is clearly documented in the study consent.

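### The primary 'intention-to-treat' analysis drops women withdrawn after randomisation, partly on undefined grounds, in an unmasked non-inferiority trial, and no planned analysis includes them

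*Combined protocol and SAP*

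**What the plan says.** Section 13.2 names intention-to-treat as the primary analysis. Women are to be analysed as randomised "regardless of compliance with study procedures, unless they asked to be withdrawn or were withdrawn by investigators due to safety or validity concerns". Its own example keeps a PTNS patient who misses sessions. What counts as a validity concern is not defined anywhere.

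Section 13.3 makes per protocol the secondary analysis. It includes women "only if they complete a full 12 weeks of treatment in compliance with study procedures". Section 13 describes no other analysis set, no handling of missing outcomes and no sensitivity analysis.

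Section 3 states that the trial is unmasked: "Women will be informed of the arm of the study to which they are randomized, as the intervention is unable to be masked".

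Section 15 lets a woman leave at any time and gives investigators several grounds for withdrawing her. One is her best interest: "if they believe that it is not in her best interest to continue study participation i.e., desire to undergo alternative treatment". Another is non-adherence: "Investigators may withdraw a subject if the subject is not following the study protocol". Section 12.1.1 says of PTNS women who miss sessions that "they will not be withdrawn from the study for missing sessions, and will be followed for outcomes", and section 12.1.2 has a parallel rule for TENS.

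**The concern.** An intention-to-treat comparison is protected by randomisation because membership is fixed before anyone knows how a woman fares. The exception in 13.2 gives up that protection. Whether a woman stays in the primary set depends on a decision made after randomisation by her or by an investigator, both aware of the arm. One investigator ground in section 15, wanting another treatment, may well follow a poor response. The text does not say whether that ground, or not following the protocol, counts as a validity concern. Membership of the primary set therefore cannot be determined from the plan.

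The usual safeguard is a second analysis that would expose the problem. Here the second analysis is narrower, so both omit the same women. If their OAB-q is not collected after withdrawal, it cannot be recovered later.

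At stake is the non-inferiority conclusion in either direction. Enough excess loss of poor responders from TENS could hide a real deficit. Excess loss of poor responders from PTNS could make an equally good TENS arm fail.

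**Working it through.** **1. Can any passage restore the excluded women?** No. Section 13.3 requires full compliance, so it is narrower than 13.2. Sections 12.1.1 and 12.1.2 protect only women who miss sessions. Section 15 says nothing about using scores from withdrawn women.

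**2. Do the withdrawal rules agree?** Sections 12.1.1 and 12.1.2 say that missed sessions do not lead to withdrawal. Section 15 permits withdrawal for not following the protocol. When the departure is missed sessions, the text does not say which governs.

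**3. The plan's own figures.** Section 5.3 gives 40 per group, a margin of 10 points, alpha 0.05, 80% power, 30% dropout and 114 randomised. The dropout step reproduces: 80/(1 − 0.30) = 114.3. The 40 per group cannot be checked because no SD is given. With a true difference of 0, the implied SD is 10 × √(40/2)/(z(1−α) + z(0.80)):
- one-sided 0.05: 44.72/(1.645 + 0.842) = 18.0;
- one-sided 0.025: 44.72/(1.960 + 0.842) = 16.0.

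The plan does not state sidedness.

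**4. Illustration.** From the plan: 114/2 = 57 per arm and the 10-point margin. Assumed: SD 18, one-sided 0.05, excluded women improve by 0, no other losses, and mean improvement over all randomised PTNS women of 15, 20 or 30 points.
- Retained mean = all-randomised mean/(1 − share excluded).
- Standard error = 18 × √(1/n_TENS + 1/n_PTNS), using retained numbers.
- The probability of declaring non-inferiority comes from the noncentral t distribution with noncentrality (expected difference + 10)/standard error.

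Worked case, 9 TENS and 3 PTNS exclusions, PTNS mean 20 and TENS mean 10. Retained TENS is 10/(48/57) = 11.88 and retained PTNS is 20/(54/57) = 21.11, a difference of −9.24. The standard error is 18 × √(1/48 + 1/54) = 3.57. False non-inferiority is 7.6% instead of 5%.

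True deficit of 10 points (results for PTNS mean 15, 20, 30):

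| Excluded, TENS v PTNS | Expected estimate | False non-inferiority |
|---|---|---|
| 9 v 3 | −9.90, −9.24, −7.92 | 5.3%, 7.6%, 14.3% |
| 8 v 4 | −10.32, −9.88, −9.00 | 4.2%, 5.4%, 8.6% |
| 7 v 5 | −10.74, −10.52, −10.08 | 3.2%, 3.7%, 4.8% |
| 6 v 6 | −11.18 | 2.4% |

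Truly equal arms: power is 87% at 6 v 6; 83%, 82%, 78% at 5 v 7; 78%, 74%, 66% at 4 v 8; and 72%, 66%, 51% at 3 v 9.

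**5. Sensitivity to the assumptions.**
- If excluded women improve half as much as retained women, 9 v 3 gives 5.1%, 6.0%, 8.2%, and power at 3 v 9 is 81%, 79%, 74%.
- At one-sided 0.025 with SD 16, 9 v 3 gives 2.7%, 4.3%, 9.5% against a nominal 2.5%.
- A different model assumes that excluded women fall short of retained women by the same D points in both arms, so bias = (share excluded from TENS − share excluded from PTNS) × D. Equal shares then give no bias. Shares of 20% v 10% with D from 5 to 20 give +0.5 to +2.0 points and false non-inferiority of 6.6% to 13.6%.

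**The case against.** **The clause is narrow.** Non-adherent women stay in the primary set, and asking to be withdrawn can be read as withdrawing consent, after which nothing more can be collected. This stands in part, and a reader should not infer that women who miss sessions are dropped. But that reading does not cover women withdrawn by investigators, or scores obtained before withdrawal.

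**The harm is conditional.** A reader might infer that any excess of exclusions from TENS flatters TENS. The figures do not support that: at 7 v 5 the expected deficit is overstated and false non-inferiority stays below 5%. Under these assumptions inflation needs a marked imbalance together with poor outcomes in the excluded women. The documents establish neither. Nor does the 30% dropout allowance measure exclusions under this clause. This objection stands in full.

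**Deleting the clause recovers little by itself.** Women with no post-baseline OAB-q add almost nothing to the main model. This also stands. The illustration shows the effect of missing outcomes, not the gain from the wording change alone.

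**Section 15 appears to say otherwise.** It states: "According to the 2010 CONSORT guidelines, we will analyze all participants assessed for eligibility within the study". A reader might take this as restoring the excluded women, or as contradicting 13.2. In context it is followed by documenting reasons for withdrawal, unmet eligibility criteria and reasons for declining, so it reads as loosely worded participant-flow accounting. It neither defines nor repairs the outcome set.

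**The consent form may say more.** Section 15 says that it documents the withdrawal procedure, and it was not available for this review. It may cover follow-up after stopping treatment, but it would not change the analysis set in 13.2.

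**Conclusion.** The primary set in 13.2 is wrong as written. It is labelled intention-to-treat but excludes randomised women for reasons arising after randomisation, one of them undefined, in an unmasked trial, and no planned analysis includes them. Confidence in this is high. It rests on the text and on the principle that non-inferiority should be judged on the arms as randomised, not on any calculated figure.

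The direction and size of any bias cannot be known from the documents. The percentages depend on a back-solved SD, assumed exclusion counts and assumed outcomes in excluded women. They show that the conclusion could be distorted either way under a strong imbalance, and hardly at all, or conservatively for false non-inferiority, under a mild one. A claim that the plan will produce false non-inferiority would go beyond the evidence.

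**What to change.** - In 13.2, delete the exception. Define the primary set as all randomised women in their assigned arm, using every OAB-q score collected, including those obtained before withdrawal.
- In section 15, separate stopping study treatment from withdrawing consent to follow-up, and keep collecting the OAB-q from women who still consent.
- Reconcile sections 12.1.1 and 12.1.2 with section 15 on withdrawal for not following the protocol.
- Pre-specify an analysis that keeps women with partial data, for example a mixed model on the OAB-q time points in Table 1, with the interval for the week-12 difference compared with the 10-point margin.
- Add a sensitivity analysis that worsens missing outcomes in TENS only, then in PTNS only, and reports where the non-inferiority conclusion changes. This is needed because the main model learns almost nothing from women with no post-baseline score.
- Report withdrawals by arm and by who initiated them, alongside the reasons that section 15 already plans to record.

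The cost is wording, a few more follow-up contacts and a little more analysis. The required sample size does not change. The main model brings a missing-at-random assumption, which the arm-by-arm sensitivity analysis is there to test.

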## 5. Number of Subjects

5.1. This is a single-center study at the University of New Mexico, therefore the total number of subjects at the University of New Mexico is the total number of subjects for the study.

5.2. The total number of subjects to be recruited at this site is up to 130 patients.

5.3. *Sample size calculation:* The primary outcome for this study is the change in the OAB-q total score from baseline to 3 months. We used the means and standard deviation for this questionnaire from an unpublished pilot RCT study from Walter Reed that compares PTNS and TENS for the treatment of OAB (unpublished work). We have powered the study based on a 10-point difference as significant between groups. This 10-point difference used for the power calculation is based on the previously established minimum important difference. To achieve power for this non-inferiority RCT study showing that the difference between groups is less than 10 points, we need 40 patients per group (80 total) to detect no difference with  $\alpha = 0.05$  and 80% power. Allowing for dropout of up to 30%, we will aim to randomize 114 patients, and will plan to recruit up to 130 to allow for potentially higher drop-out, as the study primary outcome is at the 12 weeks' time point. As we plan to perform both per-protocol and intention-to-treat analysis, the sample size must be met for both per-protocol and intention-to-treat analysis, with the per-protocol patients (those in the PTNS group completing at 12 treatments in a total of 13 weeks) being expected to be a lower sample size.

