PROTOCOL TITLE: INTENSE: INvestigation of TENS Efficacy versus Posterior Tibial Nerve Stimulation for overactive bladder

given a 3-day voiding diary to complete prior to starting their intervention. Urinalysis and urine culture will be obtained to rule out urinary tract infection. This is routinely done on all new patients in our clinic and would be performed on patients not participating in the study as well. Data collected in addition to the above outcome measures includes patient demographics, medical/surgical history, and contact information, which are attached as supporting documents. This information will be collected from the patient on the day of enrollment and we will review the patient's medical record if information is missing or unclear.

The randomization sequence will be generated by computer-based randomization in a sequence that preserves 1:1 randomization and also preserves allocation concealment (likely with randomly alternating block sizes of 6-10 in blocked randomization). Randomization assignments will be completed via REDCAP by a research coordinator. Randomization will only occur after consent has been signed and all baseline data has been obtained.

*12.1. Interventions:*

*12.1.1. PTNS:* Women randomized to the PTNS group will begin therapy after their baseline evaluation is complete. They will be scheduled for PTNS treatment sessions once weekly for 30 minutes, for 12 weeks total. PTNS treatment will be performed as follows:

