40 per group to detect this difference with  $\alpha = 0.05$  and 80% power. To allow for a dropout of up to 30% we will enroll up to 130 patients to account for participants who are lost to follow up. As noted above, we plan to perform both per-protocol and intention-to-treat analysis, and adequate power must be achieved for both per-protocol and intention-to-treat analysis, with the per-protocol patients (those in the PTNS group completing at 12 treatments in a total of 13 weeks) being expected to be a lower sample size and take more recruitment and study follow-up to achieve power.

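### Per-protocol is only secondary, so a failed per-protocol result would not stop a non-inferiority claim, although the plan requires adequate power in both sets

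*Combined protocol and SAP*

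**What the plan says.** Section 13.2 names the lead analysis ("We plan to perform the primary analysis as" intention-to-treat) and keeps women in their randomised group whatever their compliance, apart from those who withdraw or are withdrawn. Section 13.3 then gives per-protocol its rank: "We plan to perform a secondary analysis as" per protocol.

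The sizing text treats the two sets as equals. Section 5.3 says "the sample size must be met for both per-protocol and intention-to-treat analysis", and Section 13.4 repeats that "adequate power must be achieved for both per-protocol and intention-to-treat analysis". The aim in Section 5.3 is "showing that the difference between groups is less than 10 points".

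Sections 12.1.1 and 12.1.2 keep women who miss sessions in the study, follow them for outcomes and place them in the intention-to-treat set. Section 1.2.3 hypothesises better compliance with TENS than with PTNS.

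No section says that both sets must show non-inferiority, or how a disagreement is to be read. Section 13.1 lists t-tests, Wilcoxon rank-sum and Fisher's exact tests, and gives no confidence-interval rule for the margin.

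**The concern.** In a superiority trial, under-treated women in the intention-to-treat set usually make the result conservative. In a non-inferiority trial they can do the reverse: if they bring the arms closer together, a real deficit is diluted and the margin is easier to meet.

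That risk is concrete here. The Background describes weekly clinic visits as a barrier that can affect compliance with PTNS, and Section 1.2.3 expects the shortfall to fall on PTNS, the comparator. Under-treatment there would lower the PTNS response and favour the TENS claim. The per-protocol analysis is the planned check, and the plan asks for it to be fully powered, yet it has no part in the decision. TENS could be worse than PTNS by the full margin among women who use it as intended and still be reported as non-inferior.

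**Working it through.** **Inputs from the documents.** Margin 10 points on change in OAB-q total score; alpha 0.05, sidedness not stated; 80% power; "we need 40 patients per group (80 total) to detect no difference"; 30% dropout; 114 randomised, up to 130 recruited (Sections 5.2, 5.3 and 13.4). Allocation is "in a sequence that preserves 1:1 randomization" (Section 12).

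**Inputs that must be assumed.**
- SD: Section 5.3 says "We used the means and standard deviation for this questionnaire from an unpublished pilot RCT study" but prints no value, so it is back-solved below.
- Non-adherence among followed women: no rate is given, so 10–30% is used. The 30% dropout figure is not a measure of it.

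**Step 1: the plan's own figures.** 80/0.70 = 114.3, which agrees with 114 (rounding up would give 115). The 40 per group can only be run backwards, with a true difference of 0:

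SD = 10 × √(40/2) / (z_α + z_β)

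- One-sided 0.05: 44.72/(1.645 + 0.842) = 17.99, so SE = 17.99 × √(2/40) = 4.02.
- One-sided 0.025: 44.72/(1.960 + 0.842) = 15.96, so SE = 3.57.

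**Step 2: false non-inferiority on intention-to-treat, 40 followed per arm.** Let adherent women have a true TENS deficit of exactly 10 points, and let q be the non-adherent share. The intention-to-treat difference d is 10(1 − q) if non-adherent women show no difference between arms, and 10(1 − q/2) if they keep half the deficit. The chance of a false claim is Φ((10 − d)/SE − z_α). For q = 30% and no difference: (10 − 7)/4.02 − 1.645 = −0.90, giving 18.4%.

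| Non-adherent women | q | d | One-sided 0.05 | One-sided 0.025 |
|---|---|---|---|---|
| none | 0% | 10.0 | 5.0% | 2.5% |
| show no difference | 10% | 9.0 | 8.1% | 4.6% |
| show no difference | 20% | 8.0 | 12.6% | 8.1% |
| show no difference | 30% | 7.0 | 18.4% | 13.1% |
| keep half the deficit | 20% | 9.0 | 8.1% | 4.6% |
| keep half the deficit | 30% | 8.5 | 10.2% | 6.2% |

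The no-difference rows are the worst case of this model. It does not represent non-adherence confined to one arm, which could move d in either direction.

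**Step 3: the same situation with both sets required.** This was simulated with t intervals, per-protocol nested in intention-to-treat, 40,000 runs, 114 randomised and 30% lost. In the no-difference case with q = 10–30%, requiring both sets holds the false-claim rate at about 4–5% (one-sided 0.05) or about 2% (one-sided 0.025).

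**Step 4: the cost in power, true difference 0.** Per-protocol size per arm is 40 × (1 − q). The number to randomise for 40 per arm in that set is 80/(0.70 × (1 − q)). Each power cell gives one-sided 0.05, then one-sided 0.025.

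| q | Per-protocol per arm | Per-protocol power | Power, both sets | Randomise for 40 per arm |
|---|---|---|---|---|
| 10% | 36 | 76% / 76% | 74% / 72% | 127 |
| 20% | 32 | 72% / 71% | 69% / 67% | 143 |
| 30% | 28 | 67% / 65% | 64% / 61% | 164 |

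With 30% dropout, the ceiling of 130 leaves 91 followed women, so it tolerates 1 − 80/91 = 12% non-adherence before the per-protocol set falls below 40 per arm.

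**The case against.** The case for leaving intention-to-treat in the lead is respectable. The trial compares a home strategy with an office strategy, and adherence is part of what separates them. The per-protocol set is a post-randomisation selection with unequal thresholds: all 12 sessions within 13 weeks for PTNS, but an average of 5 days in 7 for TENS. Its bias can go either way. That stands, and it is why per-protocol should act alongside intention-to-treat and not replace it.

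Four stronger readings are tempting, and the documents do not support them.

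- **That dropout dilutes the comparison.** Section 13.4 ties the allowance to loss to follow-up. Those women have no 12-week score, no imputation is planned, and they are already removed in reaching 40 per arm. Only women who are followed but not compliant can dilute.
- **That non-compliant means untreated.** A PTNS woman leaves the per-protocol set by missing two sessions of 12, or one that is not made up. Many such women will be largely treated, so the no-difference rows are an extreme and not an estimate.
- **That shrinkage is certain.** Poor adherence to TENS alone would widen the gap and make intention-to-treat the harder test.
- **That the plan is already sized for a joint decision.** The sizing sentences concern power in each set. The 114 allows for dropout only, and Section 13.4 itself expects per-protocol to need more recruitment.

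It is also fair to say that reliance on intention-to-treat is inferred from the primary and secondary labels, because no decision rule is written. That does not answer the point: the labels are all the plan offers, and under them a failed per-protocol result changes nothing.

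**Conclusion.** The point holds. By its labels the plan rests the non-inferiority claim on intention-to-treat and gives per-protocol no consequence, while demanding adequate power in both sets. If compliance is poorer on PTNS, as the protocol expects, the bias favours the claim.

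The size is illustrative. It rests on a back-solved SD, a true deficit equal to the margin in adherent women, and an assumed non-adherence rate. On those terms false non-inferiority rises from 5% to at most about 18%, or from 2.5% to about 13%. Under the milder half-deficit assumption at 20–30% non-adherence it reaches about 8–10% or 5–6%. The documents do not show that inflation of any given size will occur. They do leave it unguarded when the safeguard is already planned, so the change is worth making before the data are analysed.

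**What to change.** State in Sections 13.2–13.3 that non-inferiority is claimed only if the confidence limit for the between-arm difference in OAB-q change lies inside 10 points in both the intention-to-treat and per-protocol sets, and that discordant results are reported as inconclusive. Give the confidence level and sidedness there, since neither is stated now.

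In Sections 5.3 and 13.4, restate the 80% power as conditional on 40 per arm in the per-protocol set, and give the SD and the non-adherence rate assumed.

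Reconcile the wording that decides who is in each set. The end of Section 12.1.2 excludes non-compliant TENS women from the per-protocol analysis of the PTNS arm, which does not fit Section 13.3. Section 15 lets investigators withdraw women for not following the protocol, whereas Section 12.1 says missed sessions do not lead to withdrawal.

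The rule needs no new measurements. Its cost is a lower chance of a positive claim: about 74–64% (one-sided 0.05) or 72–61% (one-sided 0.025) with 114 randomised, 30% dropout and 10–30% non-adherence among completers (assumed). Keeping 40 per arm in the per-protocol set would take 127–164 randomised over that range, against a ceiling of 130.
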